2.5 Heart Failure

While ifetroban has not yet been studied specifically in a heart failure population, many of the subjects enrolled in the historic cardiovascular trials had recent myocardial infarctions and would have been expected to have had a diminished LVEF. In over 1500 subjects studied with cardiovascular disease, the incidence of new heart failure was low ($\leq 1\%$) and no different between ifetroban and placebo treated subjects.

3 Study Objectives

This study will test the hypothesis that administration of the TPr receptor antagonist ifetroban will improve endothelial function by blocking the effects and generation of TXA₂ from non-platelet sources.

The objectives of this study are:

- To determine if thromboxane receptor antagonism improves endothelial function in subjects with non-platelet thromboxane generation.
- To determine if thromboxane receptor antagonism reduces non-platelet thromboxane generation.
- To determine if thromboxane receptor antagonism reduces oxidative stress, inflammation and thrombotic potential.
- To determine if thromboxane receptor antagonism alters renal prostaglandin secretion and improves renal function.

4 Study Design

The TRAP study is a phase 2b, single center, prospectively randomized, double-blinded, placebo-controlled outpatient clinical trial conducted at the UMass Medical School/UMass Memorial Medical Center. A schedule of study events is outlined in Appendix A.

4.1 Screening Phase

Patients with established cardiovascular disease on ≥ 81 mg daily ASA as part of their normal therapeutic regimen will be screened for non-platelet TXA₂ generation by measuring urine TXB₂ metabolites using either the AspirinWorks 11-dehydro Thromboxane B₂ Test Kit (Corgenix Inc., Bromfield, CO) or the essentially identical 11-dehydro Thromboxane B₂ ELISA Kit (Cayman Chemical, Ann Arbor, MI). Those with normalized values ≥ 1145 pg/mg creatine and who meet all other inclusion/exclusion criteria will be eligible for participation.

Urine TXB₂-M measured as part of a related on-going observational study of this same patient population under separate consent may be used to determine eligibility for this randomized trial.

4.2 Randomization

Eligible subjects will be randomized to receive either five 50 mg ifetroban oral capsules (250 mg total does) daily or matching placebo in a 1:1 ratio for 4 weeks. Double-blind randomization will occur at the first study visit using the UMass Flexible Randomization and Inventory Management System (FRIMS).

4.3 Study Interventional Phase

4.3.1 Study Visit 1 (Baseline Day 0, Outpatient)

- If not already done prior to this visit, subjects will be consented for the study.
- Compliance with uninterrupted daily aspirin use for the preceding 5 days will be verified.
- Baseline physical exam will be performed, vital signs will be recorded.
- Concomitant medications will be recorded.
- Baseline urine and blood samples will be obtained.
- Subjects will undergo baseline vascular testing.
- Subjects will be randomized.
- Subjects will be provided study drug enough for 35 days and instructed to take one pill daily. They will be instructed to continue all other medications, especially aspirin, as prescribed by their physician and to avoid unnecessary changes to their medical regimen.

4.3.1.1 Study Visit 2 (Interim Day 7 \pm 3 Days, Phone Contact)

- Subjects will be contacted approximately 1 week after starting study drug to monitor for compliance and possible adverse events (AE).

4.3.1.2 Study Visit 3 (Follow-up Day 28 \pm 3 Days, Outpatient)

- Subjects will take study drug on the day of the visit.

- Subjects will bring in unused study drug and pill counts will be performed.
- Physical exam will be performed, vital signs will be recorded.
- Concomitant medications will be recorded.
- Subjects will be assessed for possible AE.
- On-drug urine and blood samples will be obtained.
- On-drug physical exam with vital signs will be performed.
- On-drug vascular studies will be performed.

4.3.1.3 Study Visit 4 (Day 42 ± 3 Days, Phone Contact)

- Subjects will be contacted 2 weeks after stopping study drug to monitor for possible AE.

5 Study Population and Eligibility Criteria

5.1 Study Population

Patients suitable for this protocol are individuals with cardiovascular disease on standard aspirin therapy with elevated non-platelet thromboxane generation.

5.2 Inclusion Criteria

1. Males and females 18-80 years of age with established cardiovascular disease, defined by either:
 - a. Angiographic (invasive or non-invasive) evidence of coronary atherosclerosis.
 - b. Prior myocardial infarction.
 - c. Positive stress test with documented peripheral or cerebrovascular disease.
2. Taking ≥ 81 mg daily ASA as part of their standard medical regimen.
3. Urine TXB₂-M > 1145 pg/mg creatinine during screening.
4. Able to provide written consent and comply with protocol-specific procedures.

5.3 Exclusion Criteria

1. Chronic oral anticoagulation with a non-vitamin K antagonist.
2. Anticipated change or interruption in aspirin therapy during the study period.
3. STEMI within 30 days.
4. Cardiac surgery within 30 days.
5. Stage 4-5 kidney failure or on renal replacement therapy.
6. An uncontrolled ongoing severe inflammatory condition.
7. Pregnant, intending to become pregnant or breast feeding. (All women of child-bearing potential must have a negative pregnancy test within 24 hours of randomization.)
8. Known ifetroban or aspirin sensitivity.
9. Inability to perform vascular testing or comply with study protocol.
10. Participation in another investigational drug trial within 30 days of randomization.

6 Recruitment and Screening Procedures

6.1 Common Recruitment Procedures

Patients referred to the UMass Memorial Medical Center Heart and Vascular Interventional Laboratory for clinically-indicated cardiac catheterization who are participating in an ongoing observational clinical study (IRB #H00014594_3) will form the major screening population for this interventional trial. As part of this observational study, non-platelet thromboxane generation is assessed in each subject by measuring urine TXB₂-M. Subjects not participating in this screening study but who otherwise meet all the inclusion/exclusion criteria will be eligible to participate in this interventional trial.

6.2 Estimated Enrollment Period

This study will enroll a maximum of 57 subjects over a period of 30 months.

6.3 Informed Consent Procedures

Designated study personnel will explain to eligible subjects the purpose of the study, interventions, risk and benefits of participation and will answer questions. Wherever possible, subjects will be provided a copy of the UMass IRB approved consent form to review in advance of meeting with study personnel. All subjects who sign consent forms will be provide a full copy of the signed and executed document.

6.4 Confidentiality and HIPAA Requirements

All information collected on study participants will be stored in a confidential manner. Only approved study personnel will have access to data collected as part of the study. Consented study participants will be identified by a participant ID number on all study documents. Data will be stored securely using procedures described under Data Management.

6.5 Protection of Human Subjects

Protections for human subjects of research are required under Department of Health and Human Services regulations in 21 CFR parts 50, 56, and 312.

6.6 Summary of Risks and Benefits

6.6.1 Risks

6.6.1.1 Drug-related

Given its established safety profile, especially in patients with high-risk cardiovascular disease, the risks associated with ifetroban administration are expected to be minimal (see above section 2 and Investigator's Brochure). Given that both ifetroban and ASA inhibit TXA₂-mediate platelet activation, they have similar antiplatelet effects and bleeding risk.

Administration of ifetroban to subjects already taking ASA has not been shown to increase the risk of bleeding as the TXA₂ pathway in platelets is already maximally suppressed.

6.6.1.2 Blood draws

The risks of drawing blood include bleeding at the puncture site, bruising and pain. These would be expected to occur in a very small portion of the population.

6.6.1.3 Vascular Studies

The risks of vascular studies include discomfort in the arm during prolonged blood pressure cuff inflation.

7 Study Drug Handling

7.1 Drug Dispensing

50 mg ifetroban oral capsules and matching placebo will be provided by Cumberland Pharmaceuticals Inc. and packaged by the UMass Investigational Pharmacy into plastic bottles containing 175 pills. Bottle labels will contain instructions to take one pill daily in the morning, the name and contact information of the PI as well as a code that can be used in case of emergency unblinding.

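### The bottle label and Visit 1 instruction say one pill daily, but the dose is five 50 mg capsules; followed literally, subjects would take 50 mg instead of 250 mg

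*Combined protocol and SAP*

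**What the plan says.** Section 4.2 (Randomization) assigns subjects to "five 50 mg ifetroban oral capsules (250 mg total does) daily or matching placebo in a 1:1 ratio for 4 weeks".

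Section 7.1 (Drug Dispensing) is consistent with that on strength and quantity. It states that "50 mg ifetroban oral capsules and matching placebo will be provided", and that these are "packaged by the UMass Investigational Pharmacy into plastic bottles containing 175 pills". It then gives the dosing instruction: "Bottle labels will contain instructions to take one pill daily in the morning".

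Section 4.3.1 (Study Visit 1) repeats the one-a-day instruction: "Subjects will be provided study drug enough for 35 days and instructed to take one pill daily".

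Two other places bear on capsule strength. Section 2.1 (Pharmacology) describes a 250 mg capsule, which is not the strength supplied under Section 7.1. The Study Design entry of the Protocol Summary can be read either as a 250 mg daily dose or as a 250 mg capsule.

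On compliance, Section 4.3.1.1 has a phone contact at Day 7 ± 3 days. At Visit 3 (Section 4.3.1.2), "Subjects will bring in unused study drug and pill counts will be performed". Appendix A schedules pill counts at Visits 1 and 3. No expected return is stated.

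**The concern.** The dose in Section 4.2 and the instructions in Sections 4.3.1 and 7.1 cannot both be followed with the product described. One pill a day would be right for a 250 mg capsule, but Sections 4.2 and 7.1 both specify 50 mg. Section 7.1 also conflicts with itself, because its bottle size fits the supply period only at five per day.

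If the wording reaches subjects uncorrected and they follow it, the active arm receives a fifth of the planned dose. A null result on the Reactive Hyperemia Index would then say nothing about 250 mg daily, and the safety data would describe a fifth of the intended exposure. The error would not show as a difference between arms, because Section 7.1 gives one label instruction for ifetroban and placebo alike.

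The compliance checks are not tied to a single number. Staff who check against Section 4.3.1 or the label would record one capsule a day as full compliance; staff who check against Section 4.2 would record it as one fifth.

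**Working it through.** **Inputs**

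- Capsule strength: 50 mg (Sections 4.2 and 7.1).
- Planned dose: 5 capsules, 250 mg daily, for 4 weeks (Section 4.2).
- Bottle: 175 capsules (Section 7.1).
- Supply: 35 days (Section 4.3.1).
- Instruction to subjects: 1 pill daily (Sections 4.3.1 and 7.1).

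**Step 1. Reproduce the plan's dose from the supply figures.** Capsules per day = 175 / 35 = 5. Daily dose = 5 × 50 mg = 250 mg. This matches Section 4.2 exactly.

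**Step 2. Apply the instruction as written.** Daily dose = 1 × 50 mg = 50 mg, and 50 / 250 = 20% of the planned dose. Over 28 days this is 28 × 50 = 1,400 mg instead of 28 × 250 = 7,000 mg. A bottle would last 175 / 1 = 175 days, not 35.

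**Step 3. Ask whether the existing pill count could tell the regimens apart.** Assume no lost capsules. Return = 175 − (capsules per day × dosing days).

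| Dosing days | Five per day | One per day |
|---|---|---|
| 28 | 175 − 140 = 35 | 175 − 28 = 147 |
| 25 to 31 (first dose Day 1, visit Day 28 ± 3, visit-day dose counted) | 50 to 20 | 150 to 144 |
| 26 to 32 (first dose Day 0, same window) | 45 to 15 | 149 to 143 |

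At 28 dosing days the gap is 147 − 35 = 112 capsules. The ranges do not overlap under either starting day, so the count can separate the two regimens if bottles come back.

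**Step 4. Effect of lost capsules.** Apparent intake = (175 − returned) / days on drug. Over 28 days, every 28 unreturned capsules add 28 / 28 = 1 per day, and a bottle not returned at all reads as 175 / 28 = 6.25 per day. Missing bottles must therefore be treated as unknown intake.

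**Step 5. Timing of the checks.** At Visit 3, "Subjects will take study drug on the day of the visit", and the on-drug vascular tests are done at that visit. An odd count then can prompt correction for later subjects only. The Day 7 call comes earlier: at the nominal days it leaves 28 − 7 = 21 days for correction, and across both windows 25 − 10 = 15 to 31 − 4 = 27 days. The protocol does not say that the call asks for capsules per day.

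**The case against.** The strongest reply is that the intended dose is not in doubt. Section 4.2 gives it both as a capsule count and as a total, and the bottle size confirms it. The one-pill wording may be left over from a version with a 250 mg capsule, as Section 2.1 suggests, although that is an inference. On this view the defect is an incomplete text update. Harm would need several steps to fail together: the phrase is copied to the label, the pharmacy packing five a day does not notice, staff follow Section 4.3.1 over Section 4.2, and the Day 7 call misses it. Section 7.1 describes the label in running text and does not reproduce it. Consent pages are not part of the text reviewed, so other instructions to subjects may exist.

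Most of this stands as a limit on the claim. It is not known that any subject took 50 mg, and that figure is a worst case. A correction at Day 7 would leave about three weeks at full dose before the endpoint, with a half-life of about 22 hours (Section 2.1).

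It does not remove the defect. A plausible origin does not make the instruction correct for the product in Section 7.1, and both stated instructions to subjects carry the wrong number. The Day 7 call is a safeguard only if the caller knows the right number, and the protocol supplies two.

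**Conclusion.** The concern holds. The protocol's stated instructions to subjects conflict with its stated dose by a factor of five, and nothing in the text reconciles them. The size, 50 mg against 250 mg daily (20%), rests on two assumptions: that the wording reaches subjects unchanged, and that they follow it literally. The documents give no dose-response data, so the resulting loss of effect cannot be quantified. No sample size, power or alpha figure is involved. It must be fixed because it is a rule for dosing subjects, it is wrong as written, and the correction is trivial.

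**What to change.** 1. In Sections 7.1 and 4.3.1, replace the one-pill instruction with *take five capsules once daily in the morning*, worded identically for both arms. The protocol text can add that each active capsule is 50 mg; omitting the strength from the instruction avoids stating an active strength on placebo bottles.
2. Reword the Protocol Summary to *250 mg (five 50 mg capsules) once daily*.
3. Check the strength and formulation in Section 2.1 against the product supplied, and correct whatever does not match.
4. At the existing Day 7 call, ask how many capsules are taken each day.
5. State the expected Visit 3 return as 175 minus 5 per dosing day (35 after 28 dosing days), and record the count before returned drug is disposed of under Section 7.2.
6. If bottles have already gone out with the one-pill label, summarise apparent daily intake as (175 − returned) / days on drug. State that lost capsules inflate it, and report unreturned bottles as unknown intake.

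The cost is protocol and label wording, one question at a planned call and one reference figure for a planned count. No visits, procedures or patients are added.

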7.2 Drug Storage, Accountability and Destruction

Study product will be stored prior to dispensing at the UMass Investigational Pharmacy at room temperature. Unused study drug will be returned by subjects at Visit 3 and disposed of by the UMass Investigational Pharmacy, which will hold all destruction documentation.

7.3 Emergency Unblinding

The UMass Investigational Pharmacy will maintain a log of study product codes that can be used in the unlikely event that emergency unblinding is required.

8 Outcome Determinations

8.1 Primary Endpoint

The primary trial endpoint will be change from baseline in on-treatment Reactive Hyperemia Index (RHI) measured by peripheral arterial tonometry (PAT) using the standard protocol described in Appendix C .

8.2 Secondary Endpoints

Secondary trial endpoints will be the change from baseline in on-treatment:

- Brachial % flow-mediated vasodilation (FMD) using the standard protocol described in Appendix B.

- Urine 11-dhTXB₂ as measured by mass spectrometry or immunoassay and normalized to urine creatinine.

8.3 Exploratory Endpoints

Exploratory trial endpoints will be the change from baseline in on-treatment:

- Urine 8-iso-PFG_{2α} as measured by immunoassay and normalized to urine creatinine.
- Plasma tissue factor as measured by immunoassay.
- Plasma ICAM-1 as measured by immunoassay.
- Plasma activated protein C as measured by immunoassay.
- hs-CRP as measured by immunoassay.
- NT pro-BNP as measured by immunoassay.
- Urine 2,3-dinor-6-ketoPGF_{1α} and ratio of 11-dhTXB₂ to 2,3-dinor-6-ketoPGF_{1α} as measured by immunoassay and normalized to urine creatinine.
- Urine TXB₂, 6-ketoPGF_{1α} and the ratio of TXB₂ to 6-ketoPGF_{1α} as measured by immunoassay and normalized to urine creatinine.
- Glomerular filtration rate as calculated by the Cockcroft-Gault formula.

9 Subject Safety

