1.4 Factors Associated with Non-platelet TXA₂ Generation

Multivariable modelling of RIGOR subjects with documented ASA-mediated suppression of platelet TXA₂ generation identified independent risk factors for non-platelet TXA₂ generation (Table 2).² Oxidative stress, as measured by urine 8-isoPGF_{2α}, was identified as the strongest risk factor for non-platelet TXA₂ generation, accounting for nearly half of the modelled effect (Figure

5). In addition to being a marker for oxidative stress, 8-iso-PGF_{2α} is also a stable circulating eicosanoid capable of activating TPr to cause vasoconstriction and potentiate agonist-induced platelet activation.³⁶ Other independent risk factors are shown in Table 2.

[figure not shown]

Figure 5. Linear regression of urine 11-dhTXB₂ to 8-isoPGF_{2α} in 228 subjects with suppressed platelet TXA₂ generation.²

Table 2. Independent risk factors for UTXB₂* identified by multivariable regression analysis.

	Standardized Coefficient	p-value	Dominance Weight
Urine 8-iso PGF_{2α} (ln pg/mg creatinine)	0.442	<0.001	0.472
Age (years)	0.239	<0.001	0.102
Female gender	0.129	0.015	0.093
White race (versus non-white)	-0.172	0.009	0.085
Statin therapy	-0.161	0.004	0.077
Creatinine (mg/dL)	-0.152	0.002	0.072
LVEF (%)	-0.113	0.032	0.048
ASA dose (81mg vs. >81 mg)	-0.145	0.004	0.052

*Normalized using natural log transform

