10.1.2 Secondary Endpoints

Data from a preliminary study conducted at UMass ([name], unpublished data) in which FMD was measured in patients after non-STEMI ACS was used for primary endpoint power calculations. In that pilot study, mean FMD was $9.6 \pm 2.0\%$ in normal controls (n=16) and $4.6 \pm 2.8\%$ in ACS patients (n=22). Based on these data, a sample size of 48 total subjects (24 each randomized to ifetroban or placebo) is required to detect a 50% increase in FMD with 80% power for an analysis of covariance of each treatment separately with a two-sided alpha=0.05. Data from the RIGOR study was used to determine the power to detect a difference in non-platelet TXA₂ generation with drug treatment.³ With a median 11-dhTXB₂ of 330 pg/mg creatinine, a 33% reduction would be to 220 pg/mg creatinine (reduction from 5.8 to 5.4 in the natural log scale) with a s.d. of 0.55 in the log scale. A sample size of 48 total subjects (24 each randomized to ifetroban or placebo) will have the ability to detect treatment group differences described above with 80% power for an analysis of covariance of each treatment separately with a two-sided alpha=0.05, assuming an $R^2 = 0.50$ with the baseline level and treatment included in the model.

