10.2 Statistical Analysis Plan

Descriptive statistics of patient characteristics will be generated using conventional methods. The main analysis of the outcome data will be a standard ANCOVA approach (SAS PROC GLM). The full model will be fit for change in RHI (or other measure of interest) as the outcome for patient i based on treatment group (as two dummy (0,1) variables: x_1, x_2), a vector of patient characteristics $x_{3,i}$, and an error term e_i : $\ln(11-dhTXB_2)_i = b_0 + b_1x_{1i} + b_2x_{2i} + b_3x_{3i} + e_i$. We will test the main effects (treatment as well as patient characteristics) included in the model with the treatment main effects always included. We will investigate interactions between patient characteristics and treatments to provide insight into the effect of these treatments on the outcomes overall and the effect in larger patient subgroups.

11 Data Management

Study data will be recorded in a Research Electronic Data Capture (REDCap) database in the secure regulated environment at the UMass Medical School. REDCap is a secure, web-based application designed to support data capture for research studies, providing 1) formatted data entry screens; 2) audit trails; 3) automated export procedures for seamless data downloads to statistical packages; 4) procedures for importing data from external sources; and 5) an Application Programming Interface that enables it to communicate with our web-based randomization system. Data will be exported from REDCap into SAS (SAS Institute) for all analysis.

12 Regulatory Issues

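### No analysis scale is fixed for the exploratory biomarkers, and for urine 11-dhTXB₂ the endpoint in 8.2 does not match the log-level equation in 10.2; log change with log baseline should be prespecified

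*Combined protocol and SAP*

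**What the plan says.** **Endpoints.** Section 8.2 covers % FMD and urine 11-dhTXB₂: "Secondary trial endpoints will be the change from baseline in on-treatment". Section 8.3 covers urine 8-iso-PGF₂α, tissue factor, ICAM-1, activated protein C, hs-CRP, NT pro-BNP, the other urine prostanoids with two ratios, and GFR: "Exploratory trial endpoints will be the change from baseline in on-treatment". No scale is given in either place.

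**Analysis.** Section 10.2: "The main analysis of the outcome data will be a standard ANCOVA approach (SAS PROC GLM"). It continues: "The full model will be fit for change in RHI (or other measure of interest) as the outcome". The equation that follows has a different left-hand side: "\ln(11-dhTXB_2)_i = b_0". Its other terms are two treatment dummies, a vector of unnamed patient characteristics and an error. Baseline is not named.

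**Logs elsewhere in the protocol.** The footnote to Table 2 (section 1.4) says of the urine thromboxane outcome: "Normalized using natural log transform". The same table enters 8-iso-PGF₂α in "ln pg/mg creatinine". Section 10.1.2 plans 11-dhTXB₂ as a fall from 5.8 to 5.4 on the natural-log scale, "with a s.d. of 0.55 in the log scale", with R² 0.50 from a model that contains the baseline level and treatment.

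**The concern.** A programmer who follows 8.3 and the model sentence in 10.2 would most naturally compute Visit 3 minus Visit 1 for each exploratory marker, as for RHI. For 8-iso-PGF₂α that departs from the scale the protocol itself uses in Table 2.

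For 11-dhTXB₂ the text supports at least three outcomes: raw change (8.2 read plainly), log change (8.2 read with 10.1.2), and log level (the 10.2 equation). Each could be run with or without baseline.

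Two things are at stake. First, an open scale can be settled after the results are seen, and the objectives on thromboxane generation, oxidative stress, inflammation, thrombotic potential and renal prostaglandins draw on these markers. Second, the planned 11-dhTXB₂ effect is a percentage reduction. A one-third fall is 1145/3 = 382 pg/mg creatinine at the entry limit and 2290/3 = 763 at twice that level. A raw mean change therefore gives more weight to subjects who start high, whereas a geometric mean ratio estimates the planned effect directly.

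**Working it through.** **1. The plan's own figure.** Inputs from 10.1.2: median 330 falling to 220 pg/mg creatinine, log SD 0.55, R² 0.50, 24 per arm, two-sided α 0.05, stated power 80%.

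- ln 330 = 5.80, ln 220 = 5.39, difference 0.405 (0.4 as rounded in the protocol). The log values are right.
- Residual SD = 0.55 × √(1 − 0.50) = 0.389.
- SE = 0.389 × √(2/24) = 0.112.
- 0.4/0.112 = 3.56, so power = Φ(3.56 − 1.96) = 94.6% (93.6% by noncentral t).

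The stated 80% is not reproduced; 15 per arm would give it. That is a separate matter and does not affect the question of scale.

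**2. Does log level versus log change matter?** With ln(baseline) as covariate it does not. The model ln V3 − ln V1 = a + b·T + c·ln V1 rearranges to ln V3 = a + b·T + (c + 1)·ln V1, so the treatment estimate b and its test are identical. Without a baseline term it matters. Using correlation ρ = √0.50 = 0.707, difference 0.4, 24 per arm and the normal approximation:

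| Model for 11-dhTXB₂ | SD | Power |
|---|---|---|
| Log level, no baseline | 0.55 | 71.2% |
| Log change, no covariate | 0.55 × √(2 × (1 − 0.707)) = 0.421 | 90.9% |
| Log outcome with log baseline | 0.389 | 94.6% |

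The missing baseline term is therefore the consequential part of the mismatch between 8.2 and 10.2.

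**3. Log change versus raw change.** Simulation of 40,000 trials per setting: log-normal baseline and follow-up, equal log SD at both visits, a constant proportional effect, 24 per arm, and ANCOVA on change with baseline on the same scale as covariate. The reduction is one third (ln ⅔ = −0.405).

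| Log SD | ρ | Source of SD | Power, log | Power, raw |
|---|---|---|---|---|
| 0.55 | 0.707 | 10.1.2 | 93.8% | 87.9% |
| 0.55 | 0.5 | 10.1.2, weaker correlation assumed | 81.8% | 74.3% |
| 0.8 | 0.707 | assumed | 67.6% | 50.1% |
| 1.0 | 0.707 | assumed | 48.3% | 29.8% |
| 1.2 | 0.707 | assumed | 36.1% | 18.7% |

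- With the protocol's rounded effect of 0.4, the first row becomes 93.1% versus 86.8%.
- A repeat run with a different random seed gave 48% versus 29–30% at SD 1.0.
- With baseline truncated at 1145 (untruncated median assumed to be 1145, SD 0.55), power is 93.8% versus 90.5%, a gap of about 3 points.

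**4. Influence of large values.** The three largest of 48 residuals carry on average 31% of the residual sum of squares on the log scale. On the raw scale they carry 45% at SD 0.55 and 60% at SD 1.0.

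**5. Test size.** With no effect, the raw-scale test rejects in 4.7% of trials at SD 0.55 and in 4.1–4.3% at SD 1.0. It is slightly conservative and does not inflate false positives.

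**The case against.** The strongest reply is that the plan nowhere says the changes are absolute. A reader might infer from 8.2, 8.3 and the model sentence that every biomarker, 11-dhTXB₂ included, is to be analysed as a raw difference. The documents do not support that. The word absolute does not appear there, the only equation written out in 10.2 has the natural log of 11-dhTXB₂ as outcome, and 10.1.2 plans the marker on that scale. For the one biomarker that is a secondary endpoint, the intended scale is evidently logarithmic. This stands. What remains for 11-dhTXB₂ is the mismatch between a change and a log level, and the unnamed baseline term.

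It can also be said that:

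- Log use is documented for two urine markers only. Nothing in the documents describes the distributions of the plasma markers or the remaining prostanoids. This stands, so the power losses at log SD 0.8 to 1.2 are illustrations, not findings about any named marker.
- The remaining markers are exploratory, with no power claim. This limits the consequence but does not remove the need to state a scale.
- A raw ratio and its reciprocal can lead to different conclusions, whereas on logs the test is the same. This has limited force here, because 8.3 fixes the direction of both ratios.
- Baseline may be meant among the patient characteristics, given that 10.1.2 assumes it. That is plausible, but 10.2 does not say so.

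**Conclusion.** The concern holds as a gap and an inconsistency. No analysis scale is prespecified for the exploratory markers, despite the protocol's own use of logs for 8-iso-PGF₂α and urine thromboxane. For 11-dhTXB₂ the endpoint in 8.2 and the equation in 10.2 do not agree.

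At the protocol's inputs the cost of raw change is modest: about 93–94% power falls to 87–88%, and the gap narrows to about 3 points with baseline truncated at 1145. This assumes log-normal data, a constant proportional effect, and that the whole R² of 0.50 comes from baseline (ρ = 0.707). A loss of about 18 to 19 points, as at log SD 1.0, applies only if a marker is that variable, and the documents give no SD to show this.

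A reader might go further and infer that raw change would make the tests invalid. The calculation does not bear that out, since the type I error stays at or below nominal. The change should be made because it is cheap, removes a choice that could otherwise follow the data, and matches the effect the protocol planned for.

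**What to change.** In 8.2, 8.3 and 10.2:

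- Define the outcome for 11-dhTXB₂, 8-iso-PGF₂α, the other urine prostanoids, both ratios and the positive concentration biomarkers (tissue factor, ICAM-1, activated protein C, hs-CRP, NT pro-BNP) as ln(Visit 3) − ln(Visit 1).
- Name treatment and ln(Visit 1) as terms in the ANCOVA, and rewrite the 10.2 equation to show them.
- Report the ifetroban/placebo geometric mean ratio with its 95% confidence interval.
- Keep RHI, % FMD and GFR on their own scales and say so. The abbreviation list defines a log-transformed RHI, but 8.1 and 10.1.1 work with RHI untransformed.

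The cost is SAP wording and programming, plus a substitution rule, fixed in advance, for values below the assay limit. No extra subjects, visits or samples are needed.
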